4.4 Blinding/Unblinding

Not applicable.

4.5 Treatment Compliance

Study drug will be administered in the clinical facility by trained medical personnel. Treatment compliance will be monitored by drug accountability, as well as by recording BMS-986156 and nivolumab administration in subjects' medical records and CRF.

4.6 Destruction of Study Drug

For this study, study drugs (those supplied by BMS or sourced by the Investigator) such as partially used study drug containers, vials and syringes may be destroyed on site.

Any unused study drugs can only be destroyed after being inspected and reconciled by the responsible BMS Study Monitor unless study drug containers must be immediately destroyed as required for safety, or to meet local regulations (e.g., cytotoxics or biologics).

On-site destruction is allowed provided the following minimal standards are met:

- On-site disposal practices must not expose humans to risks from the drug.
- On-site disposal practices and procedures are in agreement with applicable laws and regulations, including any special requirements for controlled or hazardous substances.
- Written procedures for on-site disposal are available and followed. The procedures must be filed with the site's standard operating systems and a copy provided to BMS upon request.
- Records are maintained that allow for traceability of each container, including the date disposed of, quantity disposed, and identification of the person disposing the containers. The method of disposal, ie, incinerator, licensed sanitary landfill, or licensed waste disposal vendor must be documented.
- Accountability and disposal records are complete, up-to-date, and available for the Monitor to review throughout the clinical trial period.

If conditions for destruction cannot be met the responsible BMS Study Monitor will make arrangements for return of study drug.

It is the Investigator's responsibility to arrange for disposal of all empty containers, provided that procedures for proper disposal have been established according to applicable federal, state, local, and institutional guidelines and procedures, and provided that appropriate records of disposal are kept.

4.7 Return of Study Drug

If study drug will not be destroyed upon completion or termination of the study, all unused and/or partially used study drug that was supplied by BMS must be returned to BMS. The return of study drug will be arranged by the responsible Study Monitor.

It is the Investigator's responsibility to arrange for disposal of all empty containers, provided that procedures for proper disposal have been established according to applicable federal, state, local, and institutional guidelines and procedures, and provided that appropriate records of disposal are kept.

Arrangements for the return of study drug will be made by the responsible Study Monitor.

5 STUDY ASSESSMENTS AND PROCEDURES

5.1 Flow Chart/Time and Events Schedule

Study assessments and procedures are presented in [Table 5.1-1](#), [Table 5.1-2](#), and [Table 5.1-3](#).

Table 5.1-1: Screening Procedural Outline (CA009002)

Procedure	Screening Visit (Day -28 to -1)	Day -14 to -1 Visit	Day -3 to -1 Visit	Notes
Eligibility Assessments				
Informed consent	X			A subject is considered enrolled only when a protocol specific informed consent is signed. Obtain subject number from IVRS.
Inclusion/Exclusion criteria	X			
Medical history	X			Include any toxicities or allergy related to previous treatments.
Prior systemic therapies	X			
Tobacco history/status	X			Document subject's history and current status of tobacco use.
Safety Assessments				
PE	X			If the screening PE is performed within 1 day of dosing on C1D1, then a single exam may count as both the screening and pre-dose evaluation.
Physical measurements	X			Includes height, weight
ECOG performance status	X			See Appendix 2
Vital signs	X			Includes body temperature, respiratory rate, seated blood pressure and heart rate. Blood pressure, respiratory rate and heart rate should be measured after the subject has been resting quietly for at least 5 minutes.

Table 5.1-1: Screening Procedural Outline (CA009002)

Procedure	Screening Visit (Day -28 to -1)	Day -14 to -1 Visit	Day -3 to -1 Visit	Notes
Oxygen saturation	X			Pulse oximetry collected at rest. Oxygen levels will be used in combination with clinical signs and symptoms and radiographic images to evaluate pulmonary/respiratory status. Changes in O ₂ levels will not be used in isolation to document or diagnosis pulmonary toxicity.
ECGs	X			12-lead ECGs should be recorded after the subject has been supine for at least 5 minutes.
Laboratory Tests				Laboratory tests listed below must be completed within 2 weeks of Day 1 unless otherwise noted.
Chemistry (excluding LFTs)		X		Includes assessments for sodium, potassium, chloride, total serum calcium, magnesium, carbon dioxide, phosphorus, BUN, creatinine, creatinine kinase, CrCl, fasting glucose, total protein, albumin, amylase, lipase, CRP, uric acid, and LDH.
Complete blood count (differential & platelets)		X		
LFT assessments		X		Includes AST, ALT, total bilirubin, direct bilirubin (only if total bilirubin is elevated) ALP and GGT (only when ALP increases to \geq grade 2).
Urinalysis		X		Urine to be checked for protein, glucose, blood, leukocyte esterase, specific gravity and pH. Microscopic examination of sediment if blood, protein, or leukocyte esterase positive on dipstick.
Thyroid function tests		X		TSH with free T3 and free T4.
Mutational and viral status	X			Document EGFR and ALK mutation status for all subjects with NSCLC non-squamous cell histology. Cervical cancer only: Sites must submit and document prior HPV status within 28 days of dosing. For subjects with unknown status, tumor tissue will be required, per inclusion criteria. Subjects must consent to HPV testing.
Serology tests	X			Within 28 days of dosing: hepatitis B surface antigen, hepatitis C antibody (if is positive reflex to hepatitis C RNA) or hepatitis C RNA. Note: Testing for HIV-1, HIV-2 must be performed at sites where mandated by local requirements.
Pregnancy test			X	WOCBP only at screening and within 24 hours prior to dosing. The serum pregnancy test may be completed on the first day of treatment provided the results are available

Table 5.1-1: Screening Procedural Outline (CA009002)

Procedure	Screening Visit (Day -28 to -1)	Day -14 to -1 Visit	Day -3 to -1 Visit	Notes
				before the start of study therapy. If performed within 24 hours of dosing on C1D1, then C1D1 pregnancy test is not required.
FSH	X			If needed to document post-menopausal status as defined in Section 3.9.3 .
Concomitant medications		X		Collected during the 2 weeks prior to C1D1.
Clinical complaints		X		Collected during the 2 weeks prior to C1D1.
Adverse Event Reporting				
Monitor for SAEs	X			All SAEs must be collected from the date of subject’s written consent until 100 days post discontinuation of dosing or subject’s participation in the study if the last scheduled visit occurs at a later time. eSAEs should be approved in the electronic capture system within 5 business days of entry.
Efficacy Assessments				
Tumor assessments	X			CT with contrast is the preferred modality (MRI if CT is not feasible). Assessment should include the chest/abdomen/pelvis at a minimum; and should include other anatomic regions as indicated by individual subject disease histories.
Brain imaging	X			Brain imaging (CT/MRI) for subjects with history or symptoms of brain metastases and who have not had brain imaging within 30 days of anticipated first study drug administration
Bone scan	X			As clinical indicated (e.g., subjects with history or symptoms of bone metastases), Bone scans will not be considered a modality for assessment for measurable disease.

Abbreviations: ALP, alkaline phosphatase; ALT, alanine aminotransferase; AST, aspartate aminotransferase; BUN, blood urea nitrogen; C1D1, cycle 1 day 1; CrCl; creatinine clearance; CRP, C-reactive protein; CT, computerized tomography; ECG, electrocardiogram; EGFR, epidermal growth factor receptor; ECOG, Eastern Cooperative Oncology Group; FFPE, formalin-fixed paraffin-embedded; FSH, follicle-stimulating hormone; GGT, gamma-glutamyl transferase, HPV, human papillomavirus; HIV, human immunodeficiency virus; IVRS, Interactive Voice Response System; LDH, lactate dehydrogenase; LFT, liver function test; MRI, magnetic resonance imaging; PE, physical examination; SAE, serious adverse event; T3, triiodothyronine; T4, thyroxine;; TSH, thyroid-stimulating hormone; WOCBP, women of childbearing potential.

Table 5.1-2: On-Treatment Procedural Outline

Procedure	Cycles 1 -13					EOT ^{a,b}	Notes
	Day 1 (± 2 days)	Day 15 (± 2 days)	Day 29 (± 2 days)	Day 43 (± 2 days)	Day 49-56		
IVRS Assignment							
IVRS assignment	X						Cycle 1 only Once subject eligibility has been confirmed, IVRS assignment can be performed within 3 days prior to first study drug administration. (Discuss with Sponsor if institutional policies and procedures require additional lead-time).
Safety Assessments							
PE	X						
Symptom-directed PE		X	X	X		X ^c	
ECOG performance status	X	X	X	X		X	ECOG score (Appendix 2)
Vital signs	X	X	X	X		X	Includes temperature, seated blood pressure, and heart rate. Blood pressure and heart rate should be measured after the subject has been seated quietly for at least 5 minutes. For BMS-986156, vital signs will be obtained before the infusion and then every 15 minutes (± 5 minutes) until 60 minutes after completion of the infusion except for Cycle 1 Day 1 and Cycle 1 Day 15 (where it will be obtained for until 120 minutes post infusion). From cycle 4-13, as long as the patient has not had previous IRRs, vital signs will be obtained before the infusion, after the infusion and at 60 minutes after the completion of the infusion. If the patient has experienced any IRR, obtain vital signs every 15 minutes (± 5 minutes) until 60 minutes after completion of the infusion. For nivolumab, vital signs will be obtained before the infusion and then every 30 minutes (±10 minutes) until the start of BMS-986156 infusion or per institution guidelines for administration of nivolumab. The 30-minute post nivolumab

Table 5.1-2: On-Treatment Procedural Outline

Procedure	Cycles 1 -13					EOT ^{a,b}	Notes
	Day 1 (± 2 days)	Day 15 (± 2 days)	Day 29 (± 2 days)	Day 43 (± 2 days)	Day 49-56		
							infusion vital signs may correspond to those pre-infusion BMS-986156 vital signs. In the event BMS-986156 administration is delayed, nivolumab vital signs will be obtained until 60 minutes after completion of the infusion. If any vital sign is abnormal (based upon clinician assessment) at the final check, the subject must be observed further for a period of time, as clinically indicated.
12-lead ECG	X						All ECG tests will be in performed in triplicates (e.g., 1 ECG test equals 3 consecutive individual 12 lead ECGs performed 5 minutes apart).
Laboratory Tests	On study labs (including pregnancy testing) to be done on site/local. Within 72 hrs prior to dosing *All labs will be done weekly for Cycle 1 only. Starting Cycle 2, all of the labs will be done bi-weekly						
Chemistry (excluding LFTs)*	X	X	X	X		X	Includes assessments for sodium, potassium, chloride, total serum calcium, magnesium, carbon dioxide, phosphorus, BUN, creatinine, creatinine kinase, glucose, total protein, albumin, amylase, lipase, CRP, LDH.
Complete blood count (differential & platelets)*	X	X	X	X		X	
LFT assessments*	X	X	X	X		X	Includes AST, ALT, total bilirubin, direct bilirubin (only if total bilirubin is elevated) ALP and GGT (only when ALP is abnormal).
Thyroid function tests*	X	X	X	X		X	To include TSH with reflex testing (free T3 and free T4) if applicable. Results should be examined by the Investigator or appropriate designee within 48 hours of dose administration.

Table 5.1-2: On-Treatment Procedural Outline

Procedure	Cycles 1 -13					EOT ^{a,b}	Notes
	Day 1 (± 2 days)	Day 15 (± 2 days)	Day 29 (± 2 days)	Day 43 (± 2 days)	Day 49-56		
Urinalysis *	X	X	X	X		X	Urine to be checked for protein, glucose, blood, leukocyte esterase, specific gravity and pH. Microscopic examination of sediment if blood, protein, or leukocyte esterase positive on dipstick.
Pregnancy test (WOCBP)	X	X	X	X		X	Serum/urine pregnancy test must be performed (urine pregnancy test: minimum sensitivity 25 IU/L or equivalent units of hCG) within 24 hours prior to administration of study drug. If the pregnancy test is positive, hold all study drugs and perform confirmatory testing. If pregnancy is confirmed, permanently discontinue all study drug and immediately notify Sponsor per Section 6.4 .
Adverse Event Reporting & Concomitant Medication Assessments^d							
Concomitant medication assessments	X	X	X	X	X	X	Review prior to dosing
Monitor for non-serious AEs	X	X	X	X	X	X	Non-serious AEs will be collected starting with the first dose of study medication and through 100 days after discontinuation of dosing.
Monitor for SAEs	X	X	X	X	X	X	All SAEs must be collected from the date of subject’s written consent until 100 days post discontinuation of dosing or subject’s participation in the study if the last scheduled visit occurs at a later time. eSAEs should be approved in in the electronic capture system within 5 business days of entry.
Sample Collection							
PK assessments	See Section 5.5 and Table 5.5.1-1						Performed in all subjects.
Immunogenicity assessments	See Table 5.5.1-1						Performed in all subjects.

Table 5.1-2: On-Treatment Procedural Outline

Procedure	Cycles 1 -13					EOT ^{a,b}	Notes
	Day 1 (± 2 days)	Day 15 (± 2 days)	Day 29 (± 2 days)	Day 43 (± 2 days)	Day 49-56		
Efficacy Assessments							
Tumor/Response assessment					X	X	By methods used at baseline. Same modality/scanner should be used for all assessments. Assessed by RECIST v1.1 (Appendix 3). Assessment must be performed prior to initiating the next cycle of treatment.
Brain imaging					X		As clinically indicated.
Bone scan					X		As clinically indicated.

Table 5.1-2: On-Treatment Procedural Outline

Procedure	Cycles 1 -13					EOT ^{a,b}	Notes
	Day 1 (± 2 days)	Day 15 (± 2 days)	Day 29 (± 2 days)	Day 43 (± 2 days)	Day 49-56		
Study Drug Administration							Details regarding preparation and administration are provided in site training materials.
Parts A, B, C, and D: BMS-986156 administration	X	X	X	X			Use vials assigned per IVRS.
Part E: BMS-986156 administration	X		X				Use vials assigned per IVRS
Parts B and D ONLY: nivolumab administration	X	X	X	X			Use vials assigned per IVRS. Nivolumab is administered ONLY for those subjects enrolled in Part B (dose escalation, combination therapy) and Part D (cohort expansion, combination therapy).
Part E ONLY: nivolumab administration	X		X				Use vials assigned per IVRS, for subjects enrolled in Part E

Abbreviations: AE, adverse event; ALP, alkaline phosphatase; ALT, alanine aminotransferase; AST, aspartate aminotransferase; BUN, blood urea nitrogen; CRP, C-reactive protein; ECG, electrocardiogram; ECOG, Eastern Cooperative Oncology Group; EOT, end of treatment; GGT, gamma-glutamyl transferase; hCG, human chorionic gonadotropin; IVRS, Interactive Voice Response System; LDH, lactate dehydrogenase; LFT, liver function test; [REDACTED] PE, physical examination; PK, pharmacokinetics; RECIST, Response Evaluation Criteria in Solid Tumor; SAE, serious adverse event; T3, triiodothyronine; T4, thyroxine; TSH, thyroid-stimulating hormone; WOCBP, women of childbearing potential.

- ^a EOT is defined as the visit where decision is made to discontinue the subject from treatment.
- ^b For subject who complete all scheduled cycles of therapy, EOT visit will be the same as the last scheduled and completed on treatment visit (e.g., Cycle 3 Day 43), and the start of week 1 safety follow-up visit.
- ^c For subjects that do not complete all scheduled cycles of therapy, EOT visit will be the most recent on-treatment visit (with all available safety and response data) and does not need to be repeated, and will be considered the start of week 1 safety follow up visit.
- ^d If there is a safety concern (e.g. Grade 3 or 4 AE, SAE, etc.), ad hoc PK and ADA sample collection would be permissible (using an Unscheduled Visit Form).

Table 5.1-3: Follow-up Procedural Outline (CA009002)

Procedure	Safety Follow-up			Notes
	FU 1 30 days ^a (± 7 days)	FU 2 60 days (± 7 days)	FU 3 100 days (± 7 days)	
Safety Assessments				
PE	X	X	X	Symptom directed only.
ECOG performance status	X	X	X	ECOG score (Appendix 2).
Vital signs	X	X	X	Includes body temperature, seated blood pressure, and heart rate. Blood pressure and heart rate should be measured after the subject has been seated quietly for at least 5 minutes.
Laboratory Tests				
Chemistry (excluding LFTs)	X	X	X	Includes assessments for sodium, potassium, chloride, total serum calcium, magnesium, carbon dioxide, phosphorus, BUN, creatinine, creatinine kinase, glucose, total protein, albumin, amylase, lipase, CRP, and LDH.
Complete blood count (differential & platelets)	X	X	X	
LFT assessment	Weekly for 8 weeks following last dose of BMS-986156 (if applicable and at 30 Day, 60 Day, 100 Day follow-up.			LFTs will be monitored weekly for 8 weeks following the last dose of BMS-986156. Includes AST, ALT, total bilirubin, Direct bilirubin (only if Total Bilirubin is elevated) ALP and GGT (only when ALP is abnormal).
Thyroid function tests	X	X	X	To include TSH with reflex testing (free T3 and free T4).
Urinalysis	X	X	X	Urine to be checked for protein, glucose, blood, leukocyte esterase, specific gravity

Table 5.1-3: Follow-up Procedural Outline (CA009002)

Procedure	Safety Follow-up			Notes
	FU 1 30 days ^a (± 7 days)	FU 2 60 days (± 7 days)	FU 3 100 days (± 7 days)	
				and pH. Microscopic examination of sediment if blood, protein, or leukocyte esterase positive on dipstick.
Pregnancy Test	X	X	X	For WOCBP; serum or urine pregnancy test may be performed (clinic urine pregnancy test: minimum sensitivity 25 IU/L or equivalent units of hCG). If positive, perform confirmatory testing. If pregnancy is confirmed, immediately notify Sponsor per Section 6.4 .
Adverse Event Reporting and Concomitant Medication Assessments				
Monitor for non-serious AEs	X	X	X	Non-serious AEs will be collected starting with the first dose of study medication and through 100 days after discontinuation of dosing.
Monitor for SAEs	X	X	X	All SAEs must be collected from the date of subject's written consent until 100 days post discontinuation of dosing or subject's participation in the study if the last scheduled visit occurs at a later time. eSAEs should be approved in the electronic capture system within 5 business days of entry.
Concomitant medication assessments	X	X	X	
Sample Collection^b				
PK assessments	See Table 5.5.1-1			

Table 5.1-3: Follow-up Procedural Outline (CA009002)

Procedure	Safety Follow-up			Notes
	FU 1 30 days ^a (± 7 days)	FU 2 60 days (± 7 days)	FU 3 100 days (± 7 days)	
Immunogenicity (ADA) assessments	See Table 5.5.1-1			
Efficacy Assessments				
Tumor/Response assessments			X	Diagnostic imaging required by method used at baseline; an unconfirmed PR or unconfirmed CR must be confirmed ≥ 4 weeks after initial assessment. Same modality/scanner should be used for all assessments. Assessed by RECIST v1.1 (Appendix 3).
New anti-cancer therapies	X	X	X	Any new anti-cancer therapies (including surgery and radiotherapy) will be recorded.

Abbreviations: AE, adverse event; ALP, alkaline phosphatase; ALT, alanine aminotransferase; AST, aspartate aminotransferase; BUN, blood urea nitrogen; CR, complete response; CRP, C-reactive protein; ECG, electrocardiogram; ECOG, Eastern Cooperative Oncology Group; EOT, end of treatment; FU, follow up; GGT, gamma-glutamyl transferase; hCG, human chorionic gonadotropin IVRS, Interactive Voice Response System; LDH, lactate dehydrogenase; LFT, liver function test; PE, physical examination; PK, pharmacokinetics; PR, partial response; Q12W, every 12 weeks; RECIST, Response Evaluation Criteria in Solid Tumor; SAE, serious adverse event; SD, stable disease; T3, triiodothyronine; T4, thyroxine; TSH, thyroid-stimulating hormone; WOCBP, women of childbearing potential.

^a Follow-up visits at Days 30, 60, and 100 (± 7 days) should occur after the last dose or coinciding with the date of discontinuation ±7 days if date of discontinuation is greater than 30 days after the last dose to monitor for AEs.

^b If there is a safety concern (eg, Grade 3 or 4 AE, SAE, etc.), ad hoc PK and ADA sample collection would be permissible (using an Unscheduled Visit Form).

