BLRM with overdose control (EWOC) principle¹⁴⁴ will be employed to ensure that safety is not compromised during dose escalation. In addition, following the completion of one dose level, dose selection for next cohort/dose level will be made in conjunction with the data available on all previously dosed subjects, (including clinical and laboratory safety assessments, PK, [REDACTED] data),

will not allow escalation by more than one dose level, and will be made after discussion and agreement between Investigators and Medical Monitor.

Safety Monitoring on Study Therapy (Parts A-F)

In the absence of a pre-clinically defined safety signal, safety monitoring, by way of complete blood counts and chemistry (including liver enzyme) tests will be carried out prior to administration of study therapy, on a weekly basis for the first cycle and bi-weekly thereafter. In addition, complete physical examinations (PEs) will be conducted on Day 1 of each new cycle, along with bi-weekly symptom-directed targeted PEs prior to each administration of study drug.

In a pre-clinical mouse study in which a rat anti-GITR antibody was repeatedly administered anaphylactoid reactions were observed due to the development of IgE antibodies.¹⁴⁵ As noted in the nonclinical studies [REDACTED], BMS-986156 repeatedly administered to cynomolgus monkeys did not induce infusion-related or anaphylactoid reactions. However, because of the as yet unknown potential of infusion reactions with the administration of BMS-986156 in humans, all subjects receiving first 2 doses of BMS-986156 monotherapy and in combination with nivolumab, will be closely monitored until 120 minutes post infusion for potential infusion reactions that could occur after either first administration, or from repeat dosing of a novel monoclonal antibody. In addition, detail guidance management and algorithms for IRRs are provided in the protocol and the administration of BMS-986156 as monotherapy or in combination with nivolumab will occur at sites with medical monitoring and capability to manage infusion reaction or anaphylaxis.

Due to the potential risk of amplification of antigen-specific T-cell responses and exaggerated inflammatory response, subjects with auto-immune disorders who are at risk for flare of auto-immunity, as well as those with viral infection (human immunodeficiency virus [HIV], Hepatitis B or C) at risk for exaggerated anti-viral inflammatory response will be excluded (see [Section 3.9.2](#)).

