- 2 subjects on 30 mg BMS-986156/240 mg nivolumab: pyrexia and pruritus in 1 subject and pyrexia, hypomagnesemia, arthralgia, and appetite decreased in 1 subject, all Grade 1.
- 6 subjects on 100 mg BMS-986156 /nivolumab 240 mg: Grade 1 pyrexia, rigors, IRR, and elevated lipase. One subject experienced Grade 2 nausea, vomiting, and weight loss. One subject experienced Grade 3 elevated lipase, elevated amylase, myalgia and dry mouth all Grade 1. One patient experienced arthralgia, grade 2. One subject experienced a Grade 3 lung infection
- 13 subjects on 240 mg BMS-986156/240 mg nivolumab: Grade 1 pyrexia, headache, chills malaise, arthralgia, fatigue, myalgia diarrhea, dry mouth, hypertension, Grade 2, fatigue, cough, myalgia, decrease neutrophil count and peripheral sensory neuropathy.. Grade 3, fatigue.

Each subject treated with 30 mg BMS-986156 and 240 mg nivolumab experienced Grade 1-related IRRs (fever/pyrexia, rigors, chills, nausea, night sweats) following the first dose administered within 24 hours of the infusion. These events resolved with the oral administration of acetaminophen 500 mg. The IRRs did not recur upon subsequent dosing apart from in exception of 1 subject that experienced an additional related Grade 1 IRR after the third dose was administered (also resolved with acetaminophen 500 mg).

Two of the 9 subjects dosed with 100 mg BMS-986156/240 mg nivolumab experienced an IRR following the first dose administered within 24 hours of the infusion. These events resolved with the oral administration of acetaminophen 500 mg. These IRRs did not recur upon subsequent dosing. Six of the 27 subjects on 240 mg BMS-986156/240 mg nivolumab experienced an IRR following the first dose administered within 24 hours of the infusion. This event resolved with the oral administration of acetaminophen 500 mg. 6 of the 34 subjects (17.6%) on monotherapy experienced IRR, (1 subject on 100 mg BMS 986156, 3 on 240 mg BMS 986156 and 3 on 800 mg BMS 986156). 14 of the 50 subjects on combination therapy (28%) experienced IRR (2 on 30 mg BMS 986156/nivolumab 240 mg, 2 on 100 mg/nivolumab 240 mg, 6 on 240 mg BMS 986156/nivolumab 240 mg and 4 on 800 mg BMS 986156/nivolumab 240 mg).

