The treatment phase consists of up to three 8-week treatment cycles. In Parts A and C, each treatment cycle comprises 4 doses of BMS-986156 administered every 2 weeks on Days 1, 15, 29, and 43 of the treatment cycle. In Parts B and D, each treatment cycle comprises 4 doses of BMS-986156 (administered on Days 1, 15, 29 and 43) in combination with 4 doses of nivolumab administered on Days 1, 15, 29, and 43 of the treatment cycle. In Parts B and D and E when both study drugs are given, nivolumab will be given first followed by BMS-986156 at least 30 minutes after completion of the infusion of nivolumab. In Part E, the cohort of 480 mg/480 mg each treatment cycle comprises 2 doses of BMS-986156 (administered on Days 1 and 29) in combination with 2 doses of nivolumab administered on Days 1 and 29 of the treatment cycle.

Following each treatment cycle, the decision to treat a subject with additional cycles of study therapy, up to a maximum of 13 treatment cycles, will be based on tumor assessment (evaluation performed between Days 49 and 56 of each cycle and completed before the first dose in the next cycle). Tumor progression or response endpoints will be assessed using Response Evaluation Criteria in Solid Tumor (RECIST) v1.1 criteria for solid tumors ([Appendix 3](#)).

Treatment beyond progression may be allowed in select subjects with initial RECIST v1.1-defined progressive disease (PD) after discussion and agreement with the BMS Medical Monitor that the benefit/risk assessment favors continued administration of study therapy (e.g., subjects are continuing to experience clinical benefit as assessed by the Investigator, tolerating treatment, and meeting other criteria specified in [Section 3.11.1.1](#)).

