3.5 Cohort Expansion (Parts C, D, and E)

The purpose of cohort expansion is to gather additional safety, tolerability, preliminary efficacy, PK, [REDACTED] information regarding BMS-986156 as monotherapy or in combination with nivolumab.

Part C consists of cohort expansions with BMS-986156 monotherapy in 2 disease-restricted populations: (i) NSCLC subjects with progressive or recurrent disease (per RECIST v1.1) during or after anti-PD-1 or anti-PD-L1 therapy following prior platinum doublet-based chemotherapy and (ii) persistent, recurrent or metastatic cervical cancer.

Part D consists of cohort expansion with BMS-986156 administered in combination with nivolumab in disease-restricted populations: (i) NSCLC, (ii) cervical, (iii) bladder cancer, (iv) squamous cell carcinoma head and neck, (v) ovarian cancer, and (vi) HCC.

No more than 5 subjects previously found to be “rapid progressors” on anti-PD-1 or anti-PD-L1 therapy will be enrolled per cohort (see definition of “rapid progressors” in [Section 3.1](#)).

Each of the cohort in cohort expansion phase will contain approximately 40 subjects. (Please refer to more details in [Section 8.1.2](#)).

Parts E includes two cohorts with one as cervical and another for other solid tumors for signal seeking and exploration of Q4W dosing respectively. Due to the purpose of signal confirming in cervical cancer and heterogeneity of response rates of the other solid tumors cohort (I-O experienced NSCLC, ovarian cancer, bladder cancer, SCCHN, and HCC), approximately 40 subjects are planned for each cohort in part E. For initial safety evaluation of 480 mg BMS-986156/480 mg nivolumab Q4W 6 subjects for a safety lead-in will be enrolled and followed for a minimum of two weeks (refer to [Section 3.6](#) for the rationale for two week period) prior to opening full enrollment of Part E.

Table 3.5-1: Expansion Cohorts

Cohorts	Total Subjects (Approximate Number)
Part C: BMS-986156	
1	NSCLC
2	Cervical Cancer
Part D: BMS-986156 + Nivolumab	
3	NSCLC
4	Cervical cancer
5	Bladder
6	Squamous cell carcinoma head and neck
7	Ovarian Cancer
8	Hepatocellular
Part E: BMS-986156 + Nivolumab	
9	Cervical
10	Multiple solid tumor types

Abbreviation: NSCLC, non-small cell lung cancer.

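### The 120-minute post-infusion window in Table 5.1-2 is fixed to Cycle 1 Days 1 and 15, so Part E's second dose (Day 29) is scheduled for only 60 minutes, contrary to the first-two-doses rule in Section 1.6

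*Combined protocol and SAP*

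**What the plan says.** Section 1.6 (Overall Risk/Benefit Assessment), under a safety-monitoring heading that covers Parts A to F, sets the rule by dose number: "all subjects receiving first 2 doses of BMS-986156 monotherapy and in combination with nivolumab, will be closely monitored until 120 minutes post infusion". The stated purpose is to catch "potential infusion reactions that could occur after either first administration, or from repeat dosing of a novel monoclonal antibody".

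The vital-signs row of Table 5.1-2 (Section 5.1) sets the schedule by day. After a BMS-986156 infusion, vital signs are taken every 15 minutes until 60 minutes after completion, "except for Cycle 1 Day 1 and Cycle 1 Day 15 (where it will be obtained for until 120 minutes post infusion"). The row has no separate instruction for Part E.

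For Part E, Section 3.1 states that "each treatment cycle comprises 2 doses of BMS-986156 (administered on Days 1 and 29"). The row of Table 5.1-2 labelled "Part E: BMS-986156 administration" agrees: it is marked under Day 1 and Day 29 and blank under Days 15 and 43. Section 3.5 gives the size of Part E: "approximately 40 subjects are planned for each cohort in part E", and there are two cohorts.

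**The concern.** A rule stated by dose and a schedule stated by day agree only if the second dose falls on the named day. That is true for dosing every 2 weeks and false for dosing every 4 weeks. A site working from Table 5.1-2 would give Part E's second infusion the default 60 minutes, although the risk/benefit section relies on 120.

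The second dose is not incidental to the rule. Section 1.6 names repeat dosing as one of its two reasons for the longer window, after citing anaphylactoid reactions in mice given repeated doses of an anti-GITR antibody. The Section 1.6 safety update also reports infusion reactions in 14 of 50 combination subjects (28%). What is at stake is a stated safety commitment to Part E subjects, not any statistical result.

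**Working it through.** No published figure needs reproducing here. The check maps dose number to cycle day for each schedule and compares the window in Table 5.1-2 with the 120 minutes in Section 1.6.

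**Inputs**
- Infusion days in each cycle, Parts A to D: 1, 15, 29, 43 (Section 3.1).
- Infusion days in each cycle, Part E: 1, 29 (Section 3.1; Table 5.1-2, administration rows).
- Days with a 120-minute window: Cycle 1 Days 1 and 15. All other days default to 60 minutes (Table 5.1-2, vital signs).
- Interval between checks: 15 minutes (same row). The relaxed rule for Cycles 4 to 13 does not reach Cycle 1 Day 29.

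**Mapping**

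| Schedule | Dose | Day in Cycle 1 | Table 5.1-2 | Section 1.6 | Shortfall |
|---|---|---|---|---|---|
| Parts A to D | 1 | 1 | 120 min | 120 min | 0 |
| Parts A to D | 2 | 15 | 120 min | 120 min | 0 |
| Part E | 1 | 1 | 120 min | 120 min | 0 |
| Part E | 2 | 29 | 60 min | 120 min | 60 min |

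The days shared by {1, 15} and the first two infusion days number 2 of 2 in Parts A to D, and 1 of 2 in Part E, where the first two infusion days are {1, 29}.

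**Size**
- Scheduled post-infusion checks: 60 / 15 = 4 under the table; 120 / 15 = 8 under a 120-minute window. Shortfall: 8 − 4 = 4 checks per subject.
- Upper bound if every planned Part E subject receives dose 2: 2 × 40 = 80 subjects, 80 × 4 = 320 checks, 80 × 1 hour = 80 subject-hours.

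**Oversight or choice?** Other items were adapted to dosing every 4 weeks. Table 5.5.1-1 places the second-dose end-of-infusion sample on Cycle 1 Day 15, and Table 5.5.1-2 moves it to Cycle 1 Day 29 for Part E. Table 5.1-2 has its own Part E administration rows. Only the vital-signs note kept the 2-week days. Section 3.6.1 justifies the 14-day lead-in period after dose 1, which ends before Day 29. It says nothing about shorter observation after dose 2, and the lead-in decision is not affected.

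**The case against.** The strongest reply is that the two texts can both be obeyed. Section 1.6 speaks of close monitoring, while the table row governs how long vital signs are recorded. A site could take vital signs to 60 minutes and keep the subject under clinical observation to 120, and Section 1.6 binds sites because it is part of the protocol. This is a possible reading. However, the vital-signs row is the only scheduled procedure in the available text that carries a 120-minute window, and in Parts A to D it matches the first two doses exactly. It is evidently how the commitment was meant to be delivered.

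A second reply is that protection remains on Day 29. If any vital sign is abnormal at the final check, "the subject must be observed further for a period of time, as clinically indicated". Premedication is recommended after a Grade 1 or 2 reaction, and sites must be able to manage anaphylaxis. All of this stands and limits the harm. But the extension depends on an abnormal finding at 60 minutes, so it does not supply routine checks from 60 to 120 minutes.

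A third reply is that the reported reactions point to dose 1. For example, "Six of the 27 subjects on 240 mg BMS-986156/240 mg nivolumab experienced an IRR following the first dose". At 30 mg with nivolumab they did not recur, apart from one subject with a Grade 1 event after the third dose, and at 100 mg they did not recur. Timing is given only as within 24 hours, so nothing shows that minutes 60 to 120 are the critical ones. This stands. Timing is not given for the 800 mg combination reactions or for monotherapy.

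Finally, Part E was added by Amendment 07 in January 2017, and the current text is dated March 2019. Few or no Part E subjects may still have had a Cycle 1 Day 29 dose ahead. The documents do not say, so 80 is a planned upper bound and no more.

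**Conclusion.** The concern holds. As written, the schedule gives Part E's second BMS-986156 dose 60 minutes of post-infusion vital signs where Section 1.6 commits to 120: 4 scheduled checks instead of 8, at one visit, for up to about 80 planned subjects.

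The practical consequence is modest. The first dose keeps its full window, adverse events are collected continuously, and no endpoint, sample size, dose decision or lead-in decision changes. The documents give no infusion-reaction rate for dose 2, so no number of missed events can be stated.

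The conclusion assumes that the vital-signs row is the operational form of the Section 1.6 rule and that no unseen instruction corrects it. Site training materials and small parts of Sections 1.5 and 1.6 were not in the text available. It should still be corrected, because it is a safety commitment that the visit schedule does not carry out.

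**What to change.** Reword the exception in the vital-signs note of Table 5.1-2 by infusion number, for example:

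> *except for the first two BMS-986156 infusions (Cycle 1 Days 1 and 15 in Parts A–D; Cycle 1 Days 1 and 29 in Part E), where vital signs will be obtained until 120 minutes post infusion*

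This moves Part E's second dose from 60 to 120 minutes, brings the schedule into line with Section 1.6 and leaves Parts A to D unchanged. The cost is one table note and, for each Part E subject who receives dose 2, one extra hour with 4 more checks at a single visit.
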